4 STUDY DESIGN

4.1 OVERALL DESIGN

This is a PROBE study designed to evaluate safety, tolerability, and the ability of AMDX-2011P to detect amyloid deposits, α -syn and TDP-43 (collectively called amyloidogenic deposits) through retinal imaging, as well as PK of single bolus IV of AMDX-2011P in subjects with Parkinson's disease, MSA and ALS. Study schema is shown in Section 1.2.

The study will enroll up to 4 dose cohorts, as shown in Table 3:

Table 3 Cohorts and Planned Doses

Cohort	Number of Subjects with neurodegenerative diseases (Parkinson's Disease and/or MSA and/or ALS) ^a	Proposed dose level
1	3-9 ^b	25 mg (1 mL)
2	3-9 ^b	50 mg (2 mL)
3	12 ^b	100 mg ^c (4 mL)
4	12 ^b	150 or 200 mg ^c (6-8 mL)

Abbreviation: ALS, amyotrophic lateral sclerosis; SMC, Safety Monitoring Committee; TBD, to be determined.

a. Additional subjects (from any subject population) may be enrolled into any cohort per SMC discretion.

Approximately 9 ALS subjects will be enrolled in the study. Approximately 9 MSA subjects will be enrolled.

b. All cohorts will include 1 sentinel subject who will be observed for 8 hours and evaluated at 24 hours for safety before enrolling the remaining subjects in that cohort.

c. Tentative dose and will be confirmed by SMC based on emerging data from the prior cohorts; intermediate or higher dose level may also be explored in these cohorts.

A Safety Monitoring Committee (SMC), comprised of the Study Medical Monitor (or designee), neurologists with experience in these diseased populations, an ophthalmologist with retinal imaging expertise, and the Sponsor's clinical and technical representatives, will review safety data throughout the study. The SMC may recommend modifying the duration of observation or timing of study procedures based on safety and other available data from the first cohort. For additional details, refer to Section 10.1.5.

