All cohorts will include subjects with neurodegenerative diseases (Parkinson's disease, MSA and/or ALS). The decision to escalate to the next dose level will be made based on review of all available safety and tolerability data collected, including AEs, ECGs, vital signs, and laboratory safety results of the previous dose levels after single dose administration in at least 3 subjects from each cohort. Based on emerging data, additional cohort(s) and/or an intermediary dose may be investigated with prior approval by the SMC. The study may progress to the next cohort if approved upon satisfactory review of available safety data of the previous cohort(s) by the SMC. During each safety review, the SMC will make a decision to either continue enrollment to the next planned cohort, add additional subjects to the current cohort, or change the dose of the next cohort.

Enrollment into each cohort will begin with 1 sentinel subject who will be observed for at least 8 hours at the clinic and evaluated by the investigator at 24 hours following dosing by the investigator. If no safety issues are observed, the remaining subjects will be enrolled into that cohort. Dosing of remaining subjects at the same center will be staggered by at least 1 hour. Dosing within a cohort will continue unless stopping rules are met.

For all dose cohorts, after signing the informed consent, subjects will be screened. If needed, the screening procedures may occur over a period of up to 42 days prior to dosing. On Day 1, subjects will be admitted to the clinical research unit for 8 hours confinement. Eye examination and retinal imaging will be conducted before administration of the study drug. AMDX-2011P will be administered through a single IV bolus injection followed by repeated retinal imaging and PK and safety assessments as outlined in the Schedule of Activities (SoA; Section 1.3). On Day 8 (end of study), there will be a follow-up visit for retinal imaging and safety assessments.

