4.3 JUSTIFICATION FOR DOSE

The proposed starting dose is based on recommendations from an FDA Guidance for Industry: *Estimating the Maximum Safe Starting Dose in Initial Clinical Trials for Therapeutics in Adult Healthy Volunteers, July 2005* (FDA, July 2005). Table 4 shows NOAEL doses and systemic AUC and C_{max} exposures from the pivotal rat and dog toxicity studies, as well as projected human exposures at proposed clinical dose levels. Clinical PK parameters (clearance and volume of distribution) for AMDX-2011P were projected by model fitting of dog PK data, then scaling to human values. AMDX-2011 parameters were projected based on rates of formation and

observed metabolite/parent ratios in animals. Human PK profiles were then simulated at various doses based on projected parameter values.

The lowest NOAEL for dogs (20 mg/kg, males) equates to a human equivalent dose (HED) for a 60-kg adult male of 667 mg, and the NOAEL for systemic toxicity in rats (50 mg/kg) equates to a HED of 484 mg. Using an ~20-fold safety margin, the starting dose in the proposed clinical study will be 25 mg. The escalating doses will be 25 mg, 50 mg, 100 mg, and either 150 mg or 200 mg.

The doses proposed for this study will cover the anticipated pharmacologically active dose range and are predicted to be significantly below AUC and C_{max} exposures for AMDX-2011 and AMDX-2011P achieved at NOAEL doses in rats and dogs.

Table 4 Projected Human Dose Levels and Corresponding AUC and C_{max} Exposures Based on Nonclinical Data

Dose	AUC (hr •ng /mL)		C_{max} (ng/mL)	
	AMDX-2011P^a	AMDX-2011^a	AMDX-2011P^a	AMDX-2011^a
Human (mg)				
25	49.0	19.1	135	43.8
50	97.8	38.2	269	87.5
75	144	57.4	403	131
100	192	76.6	539	175
150	288	115	806	263
200	383	153	1070	350
Dog NOAEL^b				
20 mg/kg (Male) (HED 667 mg)	400	182	2270	937
60 mg/kg (Female) (HED 2000 mg)	13,700	2200	45,500	5930
Rat NOAEL^c				
15 mg/kg (injection site reaction) (HED 145 mg)	923	138	7,175	1,019
50 mg/kg (Systemic) (HED 484 mg)	17,900	1,345	141,500	8,930

^a human AUC and C_{max} values are estimated from projected PK at each dose level

^b NOAEL in dogs based on ophthalmic clinical observations at 60 mg/kg in males and no adverse toxicity in females. AUC values are AUC_{last}

^c NOAEL in rats based on adverse injection site reactions at 50 mg/kg, but no adverse target organ (systemic) toxicity at up to 50 mg/kg. AUC_{last} and C_{max} are means of male and female values.

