9.3.8 Interim Analyses

An exploratory interim analysis will be performed after the end of the 2nd cohort or when 12 subjects have been enrolled to assess safety, PK, and retinal image quality by SMC. Additional information will be provided in the SAP.

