10.1.5 Safety Oversight – Safety Monitoring Committee

An SMC, appointed by the Sponsor and comprised of the Study Medical Monitor (or designee), neurologists with experience in these diseased populations, an ophthalmologist with retinal imaging expertise, and the Sponsor's clinical and technical representatives, will be established before start of screening in the study. Details for the SMC will be outlined in a separate SMC Charter, the governing document that will supersede this section of the protocol. Composition of the SMC, meeting structure, schedule, and procedures, the content and format of SMC reports, and other relevant details will be determined in consultation with SMC members and detailed in a separate SMC charter.

Safety data to be reviewed by the SMC will be shared in the format of a Safety Data Review Summary. The summary will include details on any clinically significant events experienced on study related to safety parameters, with a table listing of the aggregate of AEs reported on the study. The SMC authorizes escalating the dose and continued enrolment in subsequent cohorts based on all available safety, PK and/or imaging data during the safety review.

At each decision stage, the SMC will review the Safety Data Review Summary and PK data (if available), and together make one of the following recommendations:

- To continue the study as planned, e.g. enroll the next cohort at the planned dose.
- To continue the study with modifications, e.g. modify the next dose, enroll additional subjects into current cohort, or add additional cohorts to the study
- To temporarily suspend or terminate the study. If at any time the study is terminated, a written statement fully documenting the reasons for study termination will be provided to the IRB.

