If the data permit, the terminal rate constant (λz) will be calculated. The value of λz will be determined by the slope of the regression line of the natural log transformed concentrations vs time with the following constraints:

1. At least 3 data points post the C_{max} should be used in the regression; and
2. The correlation coefficient (R^2) of regression should be > 0.80 .

To optimize the reliability of the identified terminal phase (λz), where possible, the data points used to define the λz will be manually selected. The λz profiles that do not meet the guidelines stated above will not report the AUC_{INF} , $t_{1/2}$, CL or Vz parameters for that subject profile.

When possible, AUC_{INF} will be calculated as: $AUC_{last} + (C_{last} / \lambda z)$. CL will be calculated as: $Dose / (AUC_{INF})$ and Vz will be calculated as: $Dose / (AUC_{INF} * \lambda z)$. Terminal half-life ($t_{1/2}$) will be calculated as: $\log_e(2) / \lambda z$. If the lambda z range is not at least 2-fold greater than the calculated half-life value, the half-life value will be flagged and excluded from summary descriptive statistics.

If there any deviations from the planned treatment, then the analysis model specified or methods of analysis may be re-evaluated, as appropriate. Details of any deviations from the planned analysis will be documented in the PK report.

Individual subject PK parameters will be listed and summarized by cohort / dose levels with descriptive statistics (e.g. N, arithmetic mean, SD, median, minimum, maximum, geometric mean and CV%).

Individual parameters and descriptive statistics will be presented to 3 significant figures, except N, which will be reported as whole number, while individual T_{max} and half-life values will be reported to two significant figures.

PK Figures:

Mean \pm SD Concentration vs nominal time profiles will be generated on log/linear scales by cohort.

Overlay plots of all individual plasma concentration by actual time (or nominal time) for each cohort will be generated on log/linear axis, with each subject data represented with a different symbol and included in a legend. Individual subject concentration by time plots will also be produced on log/linear axis.

Mean \pm SD AUC_{last} versus dose plots will also be generated to assess dose proportionality / linearity.

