7 INTERIM ANALYSIS

An exploratory interim analysis will be performed after the end of the 2nd cohort, or when 12 subjects have been enrolled to assess safety, PK, and retinal image quality by SMC.

Individual subject listings will be provided by Trial Runners for the following:

- subject disposition
- number of hyperfluorescent puncta pre and post dose for each subject
- TEAEs
- Clinically significant laboratory results
- Vital signs

No formal statistical analysis will be performed as the nature of the interim analysis is descriptive, to evaluate the quality of images obtained, and to inform the selection of the optimum dose. There will be no interim analysis for the MSA and Glaucoma groups.

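### At 200 mg the projected AUC is 96% and 84% of the male-dog NOAEL, not well below it, and observed 100 mg PK is not required before that step

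*Protocol*

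**What the plan says.** **Dose range and margin.** Protocol Section 4.3: "The escalating doses will be 25 mg, 50 mg, 100 mg, and either 150 mg or 200 mg". The same section says: "The doses proposed for this study will cover the anticipated pharmacologically active dose range and are predicted to be significantly below AUC" and Cmax for both analytes at NOAEL doses in rats and dogs. It makes no exception for dose, analyte, species or metric. Table 4 gives the projected human exposures and the NOAEL exposures.

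**Confirming the top doses.** Under Table 3 footnote c (Section 4.1), the Cohort 3 and 4 doses are tentative and "will be confirmed by SMC based on emerging data from the prior cohorts; intermediate or higher dose level may also be explored".

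**Data for escalation.** Section 4.1 bases the decision on "review of all available safety and tolerability data collected, including AEs, ECGs, vital signs, and laboratory safety results of the previous dose levels", in at least 3 subjects per cohort. PK is not on that list. Section 10.1.5 lets the SMC use safety, PK and/or imaging data, and says that at each decision stage "the SMC will review the Safety Data Review Summary and PK data (if available"). It also says that a separate SMC charter supersedes that section.

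**Interim look.** Protocol Section 9.3.8 places the analysis that covers PK as "performed after the end of the 2nd cohort or when 12 subjects have been enrolled". SAP Section 7 repeats that PK is to be assessed and gives the purpose as "to evaluate the quality of images obtained, and to inform the selection of the optimum dose". Its five listings are disposition, puncta counts, TEAEs, clinically significant laboratory results and vital signs.

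**PK analysis.** SAP Section 6.9 plans that mean AUC "versus dose plots will also be generated to assess dose proportionality / linearity".

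**The concern.** This is a first-in-human trial, and the last escalation has the thinnest AUC margin in Table 4. Section 4.3's text quotes margins only as human equivalent doses, 667 mg for dog and 484 mg for rat. At 200 mg those are 3.3-fold and 2.4-fold, which looks comfortable, while the AUC margin to the male-dog NOAEL is 1.04 and 1.19. An SMC member or IRB reader who relies on the text would not see this.

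The human values were simulated from parameters fitted to dog data and scaled. They rise in proportion to dose, which Section 4.3 does not state as an assumption. The rat rows rise faster than dose. Observed PK at 100 mg is the nearest check on the projection, and PK blood is already drawn from every subject. As written, the SMC may consider those data but can also escalate without them.

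**Working it through.** **Inputs (protocol Table 4; AUC in hr·ng/mL, Cmax in ng/mL)**

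| Row | AUC 2011P | AUC 2011 | Cmax 2011P | Cmax 2011 |
|---|---|---|---|---|
| Human 25 mg | 49.0 | 19.1 | 135 | 43.8 |
| Human 100 mg | 192 | 76.6 | 539 | 175 |
| Human 150 mg | 288 | 115 | 806 | 263 |
| Human 200 mg | 383 | 153 | 1070 | 350 |
| Male dog, 20 mg/kg | 400 | 182 | 2270 | 937 |
| Rat, 15 mg/kg | 923 | 138 | 7175 | 1019 |
| Rat, 50 mg/kg | 17,900 | 1345 | 141,500 | 8930 |

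**1. The plan's own figures reproduce.** With the conversion factors implied by Table 4 (dog 60 × 60/2000 = 1.8; rat 15 × 60/145 ≈ 6.2), the human equivalent doses are 20 × 60/1.8 = 667 mg and 50 × 60/6.2 = 484 mg. The starting-dose margin is 484/25 = 19.4, which matches the stated approximate 20-fold.

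**2. Projected exposure as a share of the male-dog NOAEL**

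| Dose | AUC 2011P | AUC 2011 | Cmax 2011P | Cmax 2011 |
|---|---|---|---|---|
| 100 mg | 192/400 = 48.0% | 76.6/182 = 42.1% | 23.7% | 18.7% |
| 150 mg | 288/400 = 72.0% | 115/182 = 63.2% | 35.5% | 28.1% |
| 200 mg | 383/400 = 95.8% | 153/182 = 84.1% | 47.1% | 37.4% |

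At 200 mg the AUC margins are 400/383 = 1.04 and 182/153 = 1.19. The Cmax margins are 2.1 and 2.7.

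**3. Other rows at 200 mg.** Against rat 15 mg/kg, AMDX-2011 AUC is 153/138 = 111%, above that NOAEL. Against rat 50 mg/kg the AUC margins are 17,900/383 = 47 and 1345/153 = 8.8. The female-dog AUC margins are 13,700/383 = 36 and 2200/153 = 14.

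**4. Dose-proportionality.** The log-log slope of human AUC from 25 to 200 mg is ln(383/49.0)/ln 8 = 0.99 for AMDX-2011P and ln(153/19.1)/ln 8 = 1.00 for AMDX-2011. The two-point rat exponents are ln(17,900/923)/ln(50/15) = 2.46 and ln(1345/138)/ln(50/15) = 1.89. The rat prodrug exposures lie well above the human range, so these exponents cannot be carried over to 25–200 mg in humans.

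**5. How little would close the margin**

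- Dose at which projected AUC meets the male-dog NOAEL: 400/(383/200) = 209 mg and 182/(153/200) = 238 mg. AMDX-2011 passes the rat 15 mg/kg value at 138/(153/200) = 180 mg.
- Mean 100 mg AUC that would put 200 mg at the male-dog NOAEL, assuming proportionality: 400/2 = 200 (200/192 = 1.04) and 182/2 = 91 (91/76.6 = 1.19).
- The same for 150 mg: 400/1.5 = 266.7 (266.7/192 = 1.39) and 182/1.5 = 121.3 (121.3/76.6 = 1.58).
- Break-even exponent from 100 to 200 mg if the 100 mg projection is right: log2(400/192) = 1.06 and log2(182/76.6) = 1.25.

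**6. 100 mg subjects in the interim look.** Cohorts 1 and 2 hold 3–9 subjects each. If the look follows Cohort 2, there are 0 subjects at 100 mg. If it comes at 12 enrolled, there are at most 12 − (3 + 3) = 6.

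**The case against.** The strongest reply is that this is a wording slip with narrow reach. It concerns AUC only, at one of two optional top doses, and mainly against one systemic row. A NOAEL is not a toxic threshold. The male-dog findings at 60 mg/kg were reversible eye signs, and eye examinations, vital signs, ECGs, sentinel dosing and stopping rules watch for effects directly. Section 10.1.5 already lets the SMC use PK, and the charter may require it. All of this is fair. It limits the severity but does not make the Section 4.3 statement true for AUC at 200 mg, and it does not supply a requirement in the documents at hand.

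Five technical points stand as limits:

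- Dog AUCs are to the last measurable concentration, and the type of human AUC is not stated, so the ratios are approximate.
- The 4% break-even is too fine to detect. If between-subject CV were 20–40% (an assumption; the documents give none), the standard error of a mean would be 6–12% with 12 subjects (CV/√12) and 12–23% with 3 (CV/√3). The review would catch gross misprojection, not a 4% excess.
- The rat 15 mg/kg NOAEL rests on local injection-site reactions, for which systemic AUC is a weak measure.
- SAP Section 7 says the interim covers PK, and a separate PK report is planned. The absence of PK from the five listings therefore calls for clarification and does not prove that PK is left out.
- Proportionality can be inferred from the projection method described in Section 4.3, though it is not stated there.

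**Conclusion.** The concern holds. For AUC at 200 mg, Section 4.3 misdescribes its own Table 4 (margins 1.04 and 1.19 to the male-dog NOAEL), and projected AMDX-2011 AUC is 11% above the rat 15 mg/kg value. The description is defensible for Cmax and for the female-dog and rat systemic rows, and less clearly so for AUC at 150 mg.

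Nothing in the protocol or SAP makes observed 100 mg PK a condition for 150 mg, 200 mg or the higher levels that footnote c permits. This rests on Table 4 as printed, on treating the AUC types as comparable, and on the two documents without the charter. The correction should be made. The PK review would be an inexpensive added check alongside direct safety monitoring.

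**What to change.** 1. **Protocol Section 4.3.** State that dose-proportionality is assumed. Replace the general claim with the margins to the male-dog NOAEL for AMDX-2011P and AMDX-2011: at 150 mg AUC 72% and 63%, Cmax 36% and 28%; at 200 mg AUC 96% and 84%, Cmax 47% and 37%. Note that AMDX-2011 AUC at 200 mg exceeds the rat 15 mg/kg value, and that this NOAEL reflects injection-site reactions.
2. **Protocol Sections 4.1 and 10.1.5, and the SMC charter.** For the Cohort 4 decision and any dose above 200 mg, require the SMC to review observed AUC and Cmax of both analytes through the 100 mg cohort before the dose is confirmed. Include a dose-proportionality check, using the AUC-by-dose plot already planned in SAP Section 6.9, set against the Table 4 NOAEL rows.
3. **SAP Section 7.** Add PK to the listed interim outputs.

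No dose or exposure limit is proposed; the judgement stays with the SMC. The cost is wording in four places and bioanalysis of samples already scheduled. The real downside is waiting for assay results before the last escalation; the documents give no turnaround time.

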
 To characterize the PK profile of AMDX-2011P and AMDX-2011 following administration of a single IV dose of AMDX-2011P in subjects with neurodegenerative diseases (Parkinson's disease, MSA and ALS). 	
 PK parameters of AMDX-2011P and AMDX-2011 calculated from concentrations in plasma.

Overall Study Design

This is a PROBE study designed to evaluate the safety, tolerability, and the ability of AMDX-2011P to detect amyloid deposits, α -syn and TDP-43 (collectively called amyloidogenic deposits) through retinal imaging, as well as PK of single bolus IV of AMDX-2011P in subjects with Parkinson's disease, MSA and ALS. Study schema is shown in Section 1.2.

The study will enroll up to 4 dose cohorts as follows:

Cohort	Number of Subjects with neurodegenerative diseases (Parkinson's Disease and/or MSA and/or ALS) ^a	Proposed dose level
1	3-9 ^b	25 mg (1 mL)
2	3-9 ^b	50 mg (2 mL)
3	12 ^b	100 mg ^c (4 mL)
4	12 ^b	150 or 200 mg ^c (6-8 mL)

Abbreviation: ALS, amyotrophic lateral sclerosis; SMC, Safety Monitoring Committee; TBD, to be determined.

a. Additional subjects (from any subject population) may be enrolled into any cohort per SMC discretion. Approximately 12 ALS subjects will be enrolled in the study.

b. All cohorts will include 1 sentinel subject who will be observed for 8 hours and evaluated at 24 hours for safety before enrolling the remaining subjects in that cohort.

c. Tentative dose and will be confirmed by SMC based on emerging data from the prior cohorts; intermediate or higher dose level may also be explored in these cohorts

A Safety Monitoring Committee (SMC), comprised of the Study Medical Monitor (or designee), neurologists with experience in these patient populations, an ophthalmologist with retinal imaging expertise, and the Sponsor's clinical and technical representatives, will review safety data throughout the study. The SMC may recommend modifying the duration

of observation or timing of study procedures based on safety and other available data from the prior cohorts.

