6 STUDY DRUG

6.1 STUDY DRUG(S) ADMINISTRATION

6.1.1 Study Drug Description

AMDX-2011P, a retinal tracer (small molecule), is a phosphate prodrug hydrolyzed in vivo to the pharmacologically active molecule AMDX-2011.

	Active
Study Drug Name (INN)	AMDX-2011P
Type	Retinal tracer (small molecule)
Dose Formulation	Solution for injection
Unit Dose Strength(s)	mg
Dosage Level(s)	
 • Cohort 1 – 25 mg (1 mL) • Cohort 2 – 50 mg (2 mL) • Cohort 3 – tentative 100 mg (4 mL) • Cohort 4 – tentative 150 or 200 mg (6-8 mL) 
For Cohorts 3-4, doses to be confirmed by SMC based on emerging data from prior cohorts. Intermediate and/or higher dose levels may be explored.

Route of Administration	IV bolus injection over 2 minutes
Use	Experimental
Sourcing	The drug product is manufactured by Pace (Salem, NH), and provided centrally by the Sponsor or subsidiary, or designee.
Preparation	Individual doses of AMDX-2011P will be prepared by pharmacy staff and will be provided to study personnel for administration. Procedures relating to study drug preparation will be outlined in the Pharmacy Manual. AMDX-2011P will be provided frozen (at -20°C) in a 10 mL amber vial containing 5.5 mL of solution at a concentration of 25 mg/mL. It is a single dose vial. Vials must not be shared between subjects. The solution is light sensitive and must be protected from light at all times. AMDX-2011P must be thawed to room temperature prior to administration; once thawed, it must be used within 3 hours.
Post administration instructions	Subjects to be instructed to avoid direct sun and wearing light protective eye gear such as sunglasses for 24 hours after the dose. Subjects will be evaluated for signs and symptoms of phototoxicity.
Packaging and Labeling	The study drug will be dispensed in single administration vials. Study drug will be labeled as required per local regulations. All packaging and labeling operations for the study drug will be performed according to

	Active
	current Good Manufacturing Practices and the relevant regulatory requirements.
Storage Condition	Study drug is to be stored in a secure freezer (-20°C) and monitored (manual or automated) in accordance with the labeled storage conditions with access limited to the investigator and authorized site staff.

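### Section 4.3 overstates the AUC safety margin at 200 mg (1.04- and 1.19-fold to the male-dog NOAEL in Table 4), and the protocol allows higher doses with no stated maximum

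*Protocol*

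**What the plan says.** Protocol Section 4.3 justifies the dose range in two ways.

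- **Human equivalent dose (HED).** The male-dog NOAEL of 20 mg/kg is converted to 667 mg for a 60-kg adult, and "the NOAEL for systemic toxicity in rats (50 mg/kg) equates to a HED of 484 mg". The 25 mg starting dose is described as having a margin of about 20-fold.
- **Exposure.** The proposed doses "are predicted to be significantly below AUC" and Cmax for both AMDX-2011P and AMDX-2011 at NOAEL doses in both species.

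The range itself is fixed in the same section: "The escalating doses will be 25 mg, 50 mg, 100 mg, and either 150 mg or 200 mg". Table 4 projects human exposure up to 200 mg, and the sub-study table in SAP Section 3 lists the same doses for this protocol.

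Other sections reach further. Note c of the synopsis cohort table, repeated under Table 3 in Section 4.1, says that an "intermediate or higher dose level may also be explored in these cohorts", meaning Cohorts 3 and 4, subject to SMC confirmation. Section 6.1.1 repeats it: "Intermediate and/or higher dose levels may be explored".

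**The concern.** This is a first-in-human study. Investigators, the IRB and the SMC will read Section 4.3 to learn how far the top dose lies below exposures tolerated in animals. The sentence on exposure covers every proposed dose, both analytes, both measures and both species. If one row of Table 4 shows almost no AUC margin at 200 mg, the sentence is wrong exactly where the margin matters most.

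The clause allowing higher doses adds to this. It permits dosing outside the range that Section 4.3 and Table 4 were written to support, and it gives no dose or exposure at which escalation must end.

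**Working it through.** **Inputs.** All exposures are from protocol Table 4 (AUC in hr·ng/mL, Cmax in ng/mL), in the order AMDX-2011P, AMDX-2011.

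**Step 1: reproduce the plan's own figures.** HED = NOAEL (mg/kg) ÷ species divisor × 60 kg. The divisors are not stated; Table 4 implies 1.8 (dog) and 6.2 (rat).

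- Dog: 20/1.8 × 60 = 667 mg. Rat systemic: 50/6.2 × 60 = 484 mg. Both match.
- Starting margin: 484/25 = 19.4, which is the stated margin of about 20. It is on the HED scale and applies to 25 mg only.

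**Step 2: exposure margins at 200 mg.** Margin = exposure at the NOAEL ÷ projected human exposure.

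| Comparison at 200 mg | AMDX-2011P | AMDX-2011 |
|---|---|---|
| AUC, male dog 20 mg/kg | 400/383 = 1.04 | 182/153 = 1.19 |
| AUC, rat 15 mg/kg (injection site) | 923/383 = 2.41 | 138/153 = 0.90 |
| AUC, female dog 60 mg/kg | 13,700/383 = 35.8 | 2,200/153 = 14.4 |
| AUC, rat 50 mg/kg (systemic) | 17,900/383 = 46.7 | 1,345/153 = 8.8 |
| Cmax, male dog 20 mg/kg | 2,270/1,070 = 2.12 | 937/350 = 2.68 |

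HED margins at 200 mg are 667/200 = 3.3 (male dog) and 484/200 = 2.4 (rat systemic).

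**Step 3: the same male-dog AUC margin at lower doses.**

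- 150 mg: 400/288 = 1.39 and 182/115 = 1.58.
- 100 mg: 400/192 = 2.08 and 182/76.6 = 2.38.
- 25 mg: 400/49.0 = 8.2 and 182/19.1 = 9.5, against an HED margin of 667/25 = 26.7.

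The overstatement is therefore mainly at the top dose. HED gives a male-dog margin about three times the AUC margin throughout, so quoting HED alone hides the narrower figure.

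**Step 4: look for a ceiling.** The controls in the documents are:

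- a sentinel subject in each cohort, and review "after single dose administration in at least 3 subjects from each cohort" (Section 4.1);
- SMC approval of each step (Sections 4.1 and 10.1.5);
- stopping rules driven by adverse events and laboratory findings (Section 7.1), with a list of possible next doses that includes nothing above the planned step but applies only once a stopping rule has been met;
- an interim analysis after Cohort 2 or at 12 subjects "to assess safety, PK, and retinal image quality by SMC" (Section 9.3.8), although the listings in SAP Section 7 name no PK output;
- PK at SMC reviews only where it is available (Section 10.1.5).

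None of these states a maximum dose or exposure.

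**The case against.** The strongest reply is that a NOAEL is a tested dose without an adverse effect, not the threshold for one. The male-dog NOAEL rests on eye signs at 60 mg/kg that were reversible within 6 days, and Table 4 gives no male AUC at that dose. It may be far above the NOAEL exposure: females at 60 mg/kg had AUCs 13,700/400 = 34 and 2,200/182 = 12 times the male 20 mg/kg values for a 3-fold dose step, and had no adverse toxicity. The rat 15 mg/kg NOAEL is a local injection-site finding. Cohort 4 is also tentative, at 150 or 200 mg, and needs SMC confirmation.

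All of that stands, and it limits what can be concluded. A reader might infer that 200 mg is unsafe; the documents do not show that. A reader might also extrapolate Table 4 to an exact dose at which human AUC passes the male-dog value. That would be too precise: the dog values are AUC to the last measurable concentration, the type of the projected human AUC is not stated, and the projections carry no uncertainty range.

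A second reply is that the SMC Charter may set a limit. It may. Section 10.1.5 makes the Charter the governing document for that section, and it was not available. A reader might infer that the trial has no ceiling at all; what is shown is only that the protocol and SAP state none.

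Neither reply makes the exposure sentence in Section 4.3 correct.

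**Conclusion.** The point holds as an overstated margin plus an open-ended dose clause. At 200 mg the projected AUC is 4% (AMDX-2011P) and 16% (AMDX-2011) below the male-dog NOAEL value (1 − 383/400 and 1 − 153/182), and AMDX-2011 AUC is 11% above the rat 15 mg/kg value (153/138 = 1.11). That does not fit the wording of Section 4.3. The Cmax, HED, female-dog and rat systemic margins are wider and should be reported beside it.

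The conclusion takes Table 4's projections as given and treats the dog and human AUCs as comparable. If they are of different types, the 4% figure could move either way, but the table would still not support a claim of a wide margin. The missing maximum is established for the protocol and SAP only. The change should be made, because the section concerned is the safety case for first human exposure and the correction is small.

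**What to change.** 1. **Section 4.3.** Replace the general statement on exposure with the margins at 200 mg: male dog, AUC 1.04-fold (AMDX-2011P) and 1.19-fold (AMDX-2011), Cmax 2.1- and 2.7-fold, HED 3.3-fold; rat systemic, HED 2.4-fold. Add that projected AMDX-2011 AUC exceeds the rat 15 mg/kg value (153 vs 138), and that this NOAEL reflects local injection-site reactions.
2. **Note c of Table 3 and of the synopsis cohort table, and Section 6.1.1.** State that 200 mg is the maximum dose under this version, and that any higher dose needs an amendment extending Section 4.3 and Table 4 with observed human PK. If the Charter already holds a limit, cite it instead.

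The cost is one sentence in Section 4.3 and one line in three places. Every planned dose stays as it is. The downside is that an unplanned cohort above 200 mg could be delayed, since amendments need IRB approval before they are implemented.

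I would not instead cap exposure at the male-dog AUC values (400 and 182 hr·ng/mL). Because 400/383 = 1.04, observed AMDX-2011P AUC about 5% above projection would block the planned 200 mg cohort, and nothing in the documents requires escalation to stop at that row.
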